10.1 Safety Assessments

10.1.1 Adverse Events

Adverse Event Definition

An AE is defined as any untoward medical occurrence in a clinical study subject administered a medicinal product which does not necessarily have a causal relationship with this treatment. An AE can therefore be any unfavorable and unintended sign (including an abnormal laboratory finding), symptom, or disease temporally associated with the use of a medicinal (investigational) product, whether or not it is related to the medicinal (investigational) product. This includes an exacerbation of pre-existing conditions or events, intercurrent illnesses, drug interaction or the significant worsening of the indication under investigation that is not recorded elsewhere in the eCRF under specific efficacy assessments. Anticipated fluctuations of pre-existing conditions, including the disease under study that do not represent a clinically significant exacerbation or worsening need not be considered AEs.

It is the responsibility of the investigator to document all AEs that occur during the study. AEs will be elicited by asking the subject a nonleading question, for example, "Have you experienced any new or changed symptoms since we last asked/since your last visit?" AEs should be reported in the appropriate section of the eCRF.

Assessment of Severity

Each AE will be assigned a category by the investigator as follows:

Mild:	An AE that is easily tolerated by the subject, causes minimal discomfort, and does not interfere with everyday activities.
Moderate:	An AE that is sufficiently discomforting to interfere with normal everyday activities; intervention may be needed.
Severe:	An AE that prevents normal everyday activities; treatment or other intervention usually needed.

If there is a change in severity of an AE, it must be recorded as a separate event.

Assessment of Causality

Every effort will be made by the investigator to assess the relationship of the AE, if any, to the study drug. Investigators should use their knowledge of the subject, the circumstances surrounding the event, and an evaluation of any potential alternative causes to determine whether or not an AE is considered to be related to the study drug. Causality should be assessed using the categories presented below:

- Related: Adverse event judged by the investigator as having a reasonable suspected causal relationship to the investigational medicinal product

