- Unrelated: Adverse event judged by the investigator as NOT having a reasonable suspected causal relationship to the investigational medicinal product

Action Taken

The investigator will describe the action taken in the appropriate section of the eCRF, as follows:

Action Taken:

- None
- Study Drug Stopped
- Study Drug temporarily interrupted
- Concomitant medication
- Other

Action Taken with Study Treatment:

- Dose Increased
- Dose Not Changed
- Dose Reduced
- Drug Interrupted
- Drug Withdrawn
- Not Applicable
- Unknown

Recording and Follow-up of Adverse Events

Adverse events will be recorded from informed consent to the final safety follow-up visit or the Early termination visit (if applicable). Subjects should be followed up for 3 months after receiving the last dose of study drug, and any AEs that occur during this time should be reported according to the procedures outlined above.

The subject will be followed as part of this protocol for 3 months after the last dosing.

All investigators should follow up subjects with AEs until the event is resolved or until, in the opinion of the investigator, the event is stabilized or determined to be chronic.

Documentation and Reporting of Adverse Events

AEs should be reported and documented in accordance with the procedures outlined below. All AEs occurring during the study must be documented on the relevant eCRF pages. The following data should be documented for each AE:

- Description of the symptom event
- Classification of "serious" or "not serious"
- Severity
- Date of first occurrence and date of resolution (if applicable)
- Action taken
- Causal relationship
- Outcome of event (unknown, recovered, not yet recovered, recovered with sequelae, death [with date and cause reported])

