7.3.4. Adverse Events

Adverse events will be coded using MedDRA. Adverse events will be grouped by SOC and preferred term (PT). Only treatment emergent adverse events will be summarized. Treatment Emergent Adverse Events (TEAEs) are defined as all AEs that start (or worsen) on or after the start of first study drug administration in this study and before the start of the optional treatment extension. It is assumed that AEs that started in study ND0612H-006 will not be recorded on the case report form of the present study (unless the event in question worsened during the present study), as these events will not be TEAEs in the present study. For patients who do not participate in the optional treatment extension, events that start >28 days after the last dose of study medication will not be defined as TEAEs. The summary tables will present the frequency and percentage of total subjects and number of events, by SOC and by PT.

For tables of incidence of AEs, subjects who experience the same AE (in terms of the MedDRA PT) more than once will only be counted once for that event in the number of subjects but all occurrences of the same event will be counted in the number of events.

Events with a missing start time, but with a start date equal to the date of first dose of study treatment after baseline will be considered treatment-emergent. If the AE start date is incomplete, it will be imputed as follows for the purpose of determining TEAE:

- If the start date is completely missing, the start date will be equal to the date of the first dose of study treatment. However, if the stop date is not missing and is before the date of the first dose of study treatment, then the stop date will be used instead.
- If the start day is missing, but the month and year are not missing and are equal to the month and year of the first study dose, then this event will be considered as TEAE.
- If the start day and month are missing, then the first day of the first month (January) will be used.

The original date and time will be shown on all listings of AEs. Listings will be provided for all AEs, serious AEs, AEs leading to study treatment discontinuation, AEs leading to dose adjustment/temporary withdrawal and deaths.

The following summaries will be provided:

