7.4. Tolerability and Treatment Compliance

7.4.1. Tolerability

Tolerability will be assessed based on percentage of subjects that complete the 12-month treatment period of the study and the percentage of subjects who discontinue from the 12-month treatment period due to a TEAE. Time (days) from enrolment to discontinuation will be illustrated as Kaplan-Meier curves by treatment regimen. Patients who complete the study will be right censored at the date of last dose of study treatment during the 12-month study period. Time to discontinuation will also be explored by recruitment wave 1 and 2 following corrective actions for patients' retention.

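### An AE onset known only by year is imputed to 1 January, so in the first-dose year it is classed as pre-treatment, although the same event with no date would count as a TEAE (minor)

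*SAP*

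**What the plan says.** SAP 7.3.4 has three rules for an incomplete AE start date, all for deciding TEAE status:

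1. Nothing known: "If the start date is completely missing, the start date will be equal to the date of the first dose of study treatment". If a known stop date is before first dose, the stop date is used instead.
2. Day missing, month and year present: if they "are equal to the month and year of the first study dose, then this event will be considered as TEAE".
3. Day and month missing: "If the start day and month are missing, then the first day of the first month (January) will be used". No condition refers to the first-dose year or to the stop date.

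The same section defines a TEAE as starting or worsening on or after first study drug in this study and before the optional extension. For subjects who do not enter the extension, onsets more than 28 days after last dose are excluded. It adds: "Only treatment emergent adverse events will be summarized". Tolerability (SAP 7.4.1) uses "the percentage of subjects who discontinue from the 12-month treatment period due to a TEAE".

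Protocol 11.1.4.1 gives the TEAE definition but no partial-date rule that would override these.

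**The concern.** Rules 1 and 2 resolve doubt towards treatment-emergent. In the first-dose year, rule 3 resolves it the other way. Learning the year of an event can therefore remove it from the primary safety tables, and the SAP gives no reason for this.

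The imputed date is also usually impossible for an AE that began in this study. Recording starts at informed consent (Protocol 10.1.1). That is at most 40 days before baseline for Cohort 2 (Protocol 9.1.1) and on Day 1 for Cohort 1 (Protocol 9.2.1). Cohort 1 events that began in ND0612H-006 are an exception. They are not expected on this study's case report form "unless the event in question worsened during the present study), as these events will not be TEAEs in the present study", and those that did worsen remain TEAEs.

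AEs are the primary endpoint. A new on-treatment event caught by the rule drops out of the TEAE counts and exposure-adjusted rates and, if it led to withdrawal, out of the tolerability percentage.

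**Working it through.** No figure in the plan depends on this rule, so there is none to reproduce. The check is calendar arithmetic over first-dose day d = 1 to 365.

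**Step 1: classification.** 1 January is before first dose whenever d > 1, which is 364 of 365 days (99.7%). With the date wholly missing, and no stop date before first dose, the event is a TEAE on all 365.

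**Step 2: plausibility (Cohort 2, AEs that began in this study).** 1 January is before the earliest allowed consent when 1 < d − S, with S the screening length.
- S = 40 (Protocol 9.1.1): d ≥ 42, so 324 of 365 (89%).
- S = 28 (SAP 3.1): d ≥ 30, so 336 of 365 (92%).
- Example: first dose on 15 September 2017 and onset 2017 give 1 January 2017. That is 257 days before dosing and 257 − 40 = 217 days before the earliest consent.

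**Step 3: what defaulting to first dose would wrongly count.** Assumptions: constant AE rate, evenly spread first-dose dates, T treatment days, and 91 days of follow-up with no extension (Protocol 10.1.1 records AEs for 3 months after last dose). Let R = 366 − d be the days left in the year, including the first-dose day. Recordable days in that year are:
- screening: min(S, d − 1)
- on treatment: min(T, R)
- follow-up days 1–28 (still TEAE): min(28, max(0, R − T))
- follow-up days 29–91 (not TEAE): min(91, max(0, R − T)) − min(28, max(0, R − T))

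Wrongly counted share = (mean screening + mean days 29–91) / sum of the four means. Mean screening days are 37.75 for Cohort 2 (S = 40) and 0 for Cohort 1.

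| T | On treatment | Days 1–28 | Days 29–91 | Cohort 2 share | Cohort 1 share |
|---|---|---|---|---|---|
| 365 | 183.0 | 0 | 0 | 37.75/220.75 = 17% | 0% |
| 183 | 137.38 | 12.93 | 21.23 | 58.98/209.29 = 28% | 21.23/171.54 = 12% |
| 91 | 79.78 | 19.98 | 37.11 | 74.86/174.62 = 43% | 37.11/136.87 = 27% |
| 30 | 28.81 | 24.66 | 47.64 | 85.39/138.86 = 62% | 47.64/101.11 = 47% |

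With S = 28 and T = 365 the Cohort 2 share is 26.89/209.89 = 13%. The average hides a calendar gradient: with S = 40 and T = 365 it is about 4% for January first doses and 71% for December.

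**Step 4: later years.** Take a 12-month completer who enters the extension. A year-only onset in the next calendar year becomes 1 January. That is before the extension starts, so the event counts as a main-study TEAE even if it began in the extension. With evenly spread first-dose dates, extension days in that year average 183 of 365, about 50%. Here the same bullet can raise the main-study count.

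**The case against.** **The rule may hardly ever be used.** This is the strongest objection, and it stands. In the 12 months AEs are collected on Day 2 (Cohort 2), in the early phone calls, at Week 1 and at Months 1, 2, 3, 4, 6, 9 and 12. The suggested question is "Have you experienced any new or changed symptoms since we last asked/since your last visit", the date of first occurrence is a required item (Protocol 10.1.1), and missing data are queried (Protocol 12.3). An onset whose month is unknown should be rare.

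**Affected events are not lost.** This also stands. All AEs are listed with original dates, with separate listings for serious AEs and for those leading to discontinuation. Discontinuation reasons, including the two AE categories captured in the eCRF, are tabulated under disposition (SAP 6.2) whatever the imputed onset. A reader might infer that AE withdrawals could be hidden; the documents do not support that.

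**The direction is mixed across years.** A reader might infer that the primary safety tables are biased downwards overall. Step 4 shows why that does not follow.

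**The replacement rule has its own errors.** This is correct, and they are not confined to Cohort 2 screening: late follow-up events are miscounted in both cohorts. For Cohort 2 subjects stopping at 30 days, defaulting to first dose would be wrong more often than right (62%).

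None of this explains why knowing the year should make an event less likely to count.

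**Conclusion.** As written, rule 3 contradicts rules 1 and 2 and misclassifies new on-treatment events with a year-only onset in the first-dose year (364 of 365 first-dose days). In that year it can only lower the TEAE counts. The expected effect is small: the documents give no number of year-only dates, and data collection should keep it low. Neither a material distortion of the tables nor a net bias across all years is shown.

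The rule's failure is calendar arithmetic and needs no assumption beyond the text. The shares in step 3 and the 50% in step 4 rest on the stated assumptions of a constant AE rate and evenly spread first-dose dates. They describe the cost of the remedy and the mixed direction; the finding itself does not depend on them.

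**What to change.** Replace the third bullet in SAP 7.3.4. When day and month are missing:

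- **Year equals the first-dose year:** impute the first-dose date, unless a known stop date is before first dose.
- **Year is earlier:** not a TEAE, unless the event worsened on treatment.
- **Year is later:** keep 1 January, and flag events whose possible onset range crosses the start of the extension.
- **In every case:** do not count the event as a main-study TEAE where other recorded information shows onset more than 28 days after last dose (no extension) or after the extension began.

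Report the number of AEs with year-only dates.

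The cost is one bullet and a few lines of code. The statistical price is that some first-dose-year events that are not TEAEs will be counted, in the shares tabulated in step 3. The stop-date check and the recorded-information rule remove those that can be identified. The remaining error runs towards counting, as the SAP already accepts for a wholly missing date.

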11.1.4 Primary Analyses

11.1.4.1 Methods of Analysis

Adverse events will be coded using the Medical Dictionary for Regulatory Activities (MedDRA). Adverse events will be grouped by system organ class (SOC) and preferred term (PT) and summarized by treatment regimen. Only treatment emergent AEs (TEAEs) will be summarized. TEAEs are defined as all AEs that start or worsen on or after the start of first study drug administration in the present study and before the start of the optional treatment extension (for the 1-year analysis). It is assumed that AEs that started in study ND0612H-006 will not be recorded on the case report form of the present study (unless the event in question worsened during the present study), as these

events will not be TEAEs in the present study. For subjects who do not participate in the optional treatment extension, events that start >28 days after the last dose of study medication will not be defined as TEAEs.

The summary tables will present the frequency and percentage of total subjects and number of events, by SOC and by PT.

For the summaries of AEs, subjects who experience the same AE (in terms of the MedDRA PT) more than once will only be counted once for that event in the number of subjects but all occurrences of the same event will be counted in the number of events. In addition, separate summaries will be provided for AEs by severity and relationship to study drug, as well as separate summaries for AEs leading to study drug discontinuation and SAEs.

In addition to the frequency counts and percentages, the AEs will be presented as annualized rates. The annualized rates will be calculated by the total number of reported AEs divided by the total exposure time, measured as the total subject years of exposure to the study medication.

The below listed summaries will be produced for the Safety Set. In general, all safety endpoints will be summarized using either summary statistics or frequency tabulations, as applicable to the type of data.

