5.4. Handling Withdrawals and Missing Data

In general, there will be no imputation for missing data, unless otherwise specified

The primary objective of this study is safety. Safety data will not be subject to any imputation and will be summarized on an observed case basis. For the analysis of the AEs, the incomplete follow-up will be taken into account by summarizing the data as annualized rates in addition to the

frequency counts and percentages. The analysis of the annualized rates takes into account the actual duration of the exposure to the study treatment.

For the efficacy endpoint, the missing data will be handled as follows:

- For patients who withdraw from the study, data at the early termination visit will be excluded from the by-visit summaries but will be included in the closest visit in case this visit was missing.
- For the continuous efficacy endpoints, likelihood-based modeling approach will be used to handle incomplete data. For this purpose, Mixed Model for Repeated Measures (MMRM) will be applied, see section 8.2.1.
- For categorical efficacy endpoints, the last non missing available data will be used for incomplete data.

All withdrawals will be included in all analyses up to the time of withdrawal. Subjects who are withdrawn prematurely from study drug and/or the study will be included in all analyses regardless of the duration of treatment.

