5.5. Study Days and Visit Windows

Study days will be numbered relative to the first day of study drug administration. The start of treatment (day 1) is defined as the date on which a patient takes the first dose of study drug, as recorded in CRF. Days will be numbered relative to study start (ie, ..., -2, -1, 1, 2, ...; with day 1 being the start of study drug and day -1 being the day before the start of study drug).

The study data will be summarized as collected at the scheduled study visits regardless of visit window violations. For by-visit summaries, if there are multiple assessments at a post-baseline visit, then the last non-missing assessment at that visit will be used for the summary.

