7.2. Study Drug Administration

Duration of treatment (days treated) is the number of days on treatment based on the first and last days of treatment with the study drug (last day of study drug – first day of study drug + 1).

The following information will be summarized by treatment regimen and overall.

- The number of patients exposed to study treatment
- Mean Duration of exposure (days)

- Total exposure to study treatment, expressed as person years (sum of exposure to study treatment over all patients, classified by treatment regimen)
- Number of patients who reduced ND0612 dose and the mean reduction from baseline to each visit

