7.3.1.2. Hypersensitivity Analyses

- Summaries for total Number of Hypersensitivity cases (by SOC and PT), will be presented as number of events, event rates adjusted to exposure and patient counts and percentages.
- Time to onset of Hypersensitivity will be presented by Kaplan Meier figures. In these analyses, the patients who did not experience Hypersensitivity will be right censored at the time of the last visit.
- Time from onset of Hypersensitivity to resolution will be presented with descriptive statistics. Unresolved cases will be right censored at the last visit.
- Summaries for total number of Hypersensitivity will be broken down by Outcomes (unknown, recovered, not yet recovered, recovered with sequelae and death) and will be presented as number of events, event rates adjusted to exposure and patient counts and percentages.

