- A table of the overall incidence (number and percentage) of patients reporting TEAEs and the number of TEAE events and event rates adjusted to exposure, drug-related TEAEs, severe TEAEs, serious TEAEs, TEAEs leading to study treatment discontinuation, TEAEs leading to dose adjustment/temporary withdrawal, and TEAEs leading to death
- TEAEs by SOC and PT, both as number of events, event rates adjusted to exposure and patient counts and percentages
- TEAEs by PT, both as number of events, event rate adjusted to exposure, patient counts, sorted by descending frequency of patients reporting TEAEs in Regimens 1
- Drug-related TEAEs by PT, both as event, event rate adjusted to exposure and patient counts and percentages
- Severe TEAEs by PT, both as event, event rate adjusted to exposure and patient counts and percentages

- Drug-related TEAEs by SOC, PT and severity both, as event, event rate adjusted to exposure and patient counts and percentages
- Serious TEAEs by PT, both as event, event rate adjusted to exposure and patient counts and percentages
- TEAEs leading to study treatment discontinuation, both as event, event rate adjusted to exposure and patient counts and percentages
- TEAEs leading to dose adjustment/temporary withdrawal, both as event, event rate adjusted to exposure and patient counts and percentages
- TEAEs classified by SOC, PT and the time of onset both as event, event rate adjusted to exposure and patient counts and percentages. For this summary, the time of onset will be classified as <7 days, 7-30 days or >30 days

In addition, the following analyses will be performed for the most common or relevant TEAEs (at least for the 10 most commonly reported PTs in both regimens 1 and 3 including also dyskinesia in case it is not among the 10 most common ones):

- The time to first onset of each TEAE within each treatment group will be summarized with Kaplan-Meier methods. In these analyses, the patients who did not experience the AE in question will be censored at the time of the last visit. Separate Kaplan-Meier plots (including separate curve for each treatment group) will be done for each PT.

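### TEAE rates by onset window (<7, 7-30, >30 days) have no window-specific denominator; with the only one defined, total exposure, they mainly reflect window length

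*SAP*

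**What the plan says.** Among the adverse event summaries in SAP 7.3.4 is "TEAEs classified by SOC, PT and the time of onset both as event, event rate adjusted to exposure and patient counts and percentages". The next sentence sets the categories: "For this summary, the time of onset will be classified as <7 days, 7-30 days or >30 days".

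Three other places bear on what that rate means:

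- Protocol 11.1.4.1: "The annualized rates will be calculated by the total number of reported AEs divided by the total exposure time", measured in total subject-years on study medication.
- SAP 7.2, the only exposure quantity defined: person-years as "sum of exposure to study treatment over all patients, classified by treatment regimen".
- SAP 5.4: "The analysis of the annualized rates takes into account the actual duration of the exposure to the study treatment".

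None of these is written specifically for the onset table, and none splits exposure by time since first dose. On day counting, SAP 5.5 numbers study days "with day 1 being the start of study drug and day -1 being the day before the start of study drug", but SAP 7.3.4 does not say whether the onset windows use study days or elapsed days.

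For the Kaplan-Meier curves of common events, SAP 7.3.4 says "the patients who did not experience the AE in question will be censored at the time of the last visit". SAP 7.3.1.2 has the same rule for hypersensitivity ("the patients who did not experience Hypersensitivity will be right censored at the time of the last visit"), and 7.3.1.3 repeats it for polyneuropathy. Which visit is meant is not stated.

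**The concern.** A rate by onset window invites the reader to compare risk soon after the start of infusion with risk later. That needs events in the window over subject-time in the window. If all three windows share one total, the printed rates add up to the overall rate. A long window then gets a high rate because it is long. A constant risk would print as a rising one, and a moderate early excess would be hidden.

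The study pays close attention to the first week (a Day 2 visit, calls and a Week 1 visit), and this table is the only planned display of all TEAEs by time since start, so a misleading early rate matters to a reader of the safety profile.

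**Working it through.** The plan states no figure to reproduce. The check is person-time arithmetic.

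**Inputs from the documents.** Windows <7, 7-30 and >30 days (SAP 7.3.4); a 12-month period, taken as 365 days; Day 1 is the first dose (SAP 5.5); TEAEs counted to 28 days after the last dose for subjects not entering the extension (SAP 7.3.4); about 210 treated subjects (Protocol 11.2). The SAP gives 120-170, but the ratios below do not depend on the number.

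**Assumptions.** The documents give no dropout rate, so 12-month dropout d runs from 0 to 50% with a constant hazard. Completers leave at day 365.

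**Formulas.**

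- Dropout hazard: h = -ln(1-d)/365.
- On-drug time per subject between days a and b: [exp(-ha) - exp(-hb)]/h, or b - a if d = 0.
- Understatement = total exposure / time at risk in the window.
- Break-even = time at risk after day 30 / time at risk before day 7. This is how far first-week risk must exceed later risk before the two printed rates are equal.

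**No dropout, study days.** The windows are 6, 24 and 335 days. Understatement is 365/6 = 60.8, 365/24 = 15.2 and 365/335 = 1.09. Break-even is 335/6 = 55.8. If 7-30 is read as 23 elapsed days, the middle figure is 365/23 = 15.9.

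**Range over the readings.** Elapsed-day rows use windows of 7, 24 and 334 days.

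| Day counting | Time at risk | Dropout | <7 d | 7-30 d | >30 d | Break-even |
|---|---|---|---|---|---|---|
| Study day | either | 0% | 60.8 | 15.2 | 1.09 | 55.8 |
| Study day | on drug | 50% | 44.1 | 11.4 | 1.12 | 39.2 |
| Study day | plus 28 days | 50% | 43.9 | 11.0 | 1.06 | 41.2 |
| Elapsed | either | 0% | 52.1 | 15.2 | 1.09 | 47.7 |
| Elapsed | on drug | 50% | 37.9 | 11.4 | 1.13 | 33.5 |
| Elapsed | plus 28 days | 50% | 37.6 | 11.0 | 1.07 | 35.2 |

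**Worked example.** Take 210 subjects, 40% dropout, study days and the 28-day tail. Total exposure is 164.3 subject-years. Time at risk in the windows is 3.45, 13.8 and 153.5 subject-years. These sum to more than 164.3 because the tail is off drug.

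- A constant true rate of 5 per year prints as 5 × 3.45/164.3 = 0.10, then 0.42 and 4.67.
- A falling true rate of 20, 10 and 5 per year prints as 0.42, 0.84 and 4.67, which looks like a rise.

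**Regimens within one window.** With identical true rates and dropout of 20% against 40%, the printed <7-day rates differ by a factor of 1.14; at 20% against 50%, by 1.24. That is far less than the distortion across windows.

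**Kaplan-Meier censoring.** At 40% dropout and an assumed constant hazard giving 20% true risk at 12 months, the curve ends at 20.0% if early stoppers are censored at last dose + 28 days. It ends at 20.7% if they are censored at the early termination visit, because their later events still count while they have left the risk set. It ends at 18.7% if they are censored at the 3-month visit, because they then sit in the risk set for about 91 - 28 = 63 days in which no TEAE can be counted. At 5% risk the figures are 5.0, 5.2 and 4.65%.

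**The case against.** The strongest reply is that the line is under-specified, not wrong. The subject-years formula is in the Protocol, for adverse events overall, and the Protocol does not mention an onset table. A programmer could take the SAP's wording to mean exposure within the window. This stands in part: a reader might infer that the plan prescribes the wrong division for this table, and the documents do not say so. They do leave total exposure as the only denominator defined, and nothing points to another.

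A second reply is that early risk is visible elsewhere. Kaplan-Meier onset curves are planned for hypersensitivity, polyneuropathy and at least the ten most common preferred terms, plus dyskinesia. That also stands in part, so it would be too strong to say the report would conceal early risk altogether. The curves show first onset only, do not cover the remaining terms, and none is specified for infusion site reactions as a group (SAP 7.3.1.1).

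Third, counts have the same pattern: under constant risk the >30-day count also exceeds the <7-day count about 33-56 fold. This is correct. The counts remain valid as counts, but removing the rate column would remove only the misleading label.

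Fourth, Day 1 is not first exposure for Cohort 1 subjects who come straight from ND0612H-006 (Protocol 9.2.1). This also stands. That cohort is limited by the 36 subjects to be treated in that study (Protocol 11.2), and the fix should separate the direct rollovers.

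**Conclusion.** The point holds for one descriptive table. With the only denominator defined, the <7-day rate is understated about 38-61 fold and the 7-30-day rate about 11-16 fold, while the >30-day rate is nearly right. The break-even excess is about 33-56 fold. These ranges cover 0-50% assumed dropout, both ways of counting days, and on-drug time or a 28-day tail; window length dominates under every variant.

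A reader might infer that the primary safety results are affected. They are not: overall TEAE rates and the rates for infusion site reactions, hypersensitivity and polyneuropathy use total exposure properly, and the onset table is not a named primary analysis. Comparison of regimens within a window is largely preserved when dropout is similar.

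Nor do the documents support a claim of material bias in the Kaplan-Meier curves. The censoring visit is undefined, but Safety Follow-up 1, four weeks after last treatment and with adverse event recording (Protocol 8.1.2 and 9.2.4), is a natural reading with almost no bias. The other readings move the curve by about +0.7 or -1.3 percentage points in the 20% example.

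**What to change.** In SAP 7.3.4:

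- Divide each window's events by the subject-time at risk inside that window, and state whether <7 days means study days or elapsed days.
- Show events with a fully imputed start date separately. SAP 7.3.4 sets a completely missing start date to the first-dose date (unless a known stop date precedes it) in order to decide TEAE status. If that date also sets the window, such events fall in the first week, where each adds about 1/3.5 = 0.29 per year, against 1/164 = 0.006 on total exposure.
- Show Cohort 1 direct rollovers separately.

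As a fallback, drop the rate column from this table and note that the counts scale with window length.

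As a minor clarification in 7.3.1.2, 7.3.1.3 and 7.3.4, censor event-free subjects at the earliest of last dose + 28 days, start of the extension, or last contact.

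The cost is SAP wording and programming, with no new data and no change to overall rates. The downside is imprecision: the first-week denominator is only about 3.5-4 subject-years for 210 subjects, so rates by preferred term and regimen will be unstable and are best printed beside the counts.
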